13.3 Accrual and Feasibility

Sample size: Intervention = 80 (40 statin: 40 placebo) randomized sample; Analytic sample = 72 (36:36)

after 10% drop-out. The expected accrual rate is 6-7 participants per month across four study sites, and the planned recruitment duration is 12 months. We anticipate that all evaluable participants will have completed all study procedures within 24 months. Power and precision arguments are provided below.

Accrual was calculated based on the number of liver transplant candidates actively registered at CSMC, NWU, GU, and UPR at a given time in addition to the number of new candidates expected to be registered over a 12-month period. Cirrhotics who are eligible and not listed for transplant may also be recruited.

13.4 Primary Objective, Endpoint(s), Analysis Plan

The primary outcome for this study is change from baseline to 6 months in AFP-L3%. Power calculations are presented in Table 2. In the treatment group, we expect change of 2.8 over 6 months, and in the

	Table 2. Numeric Results for Mann-Whitney Test									
a change of 0, with	Power	N1	N2	Ratio	Alpha	Beta	Mean1	Mean2	S1	S2
standard deviation=5.3 in	0.81	36	36	1	0.1	0.19	2.8	0	5.3	5.3
both groups (or smaller). Null Hypothesis: Mean1=Mean2. Alternative Hypothesis: Mean1>Mean2.										
For a Phase II study we The standard deviations were assumed to be unknown and unequal.										

have an acceptable alpha of 10%. For the primary endpoint, AFP-L3%, we will consider changes D(T) and D(P) for D=After-Before, for simvastatin (T) and placebo (P) groups, respectively. We will use a nonparametric two-sample Wilcoxon-Mann-Whitney test to address the hypothesis H0: mean [D(T)] =mean [D(P)] versus H1: means[D(T)] > mean [D(P)] and report a defined one-sided p-value. If p<0.1 we will consider this to be evidence of an effect of simvastatin on AFP-L3%. If p>0.1 we will report the actual means and the corresponding confidence intervals observed and declare the trial had failed. If we observe: mean[(D(P)] > mean[D(T)] which would be unexpected, we will declare the trial failed and discuss possible explanations for the observed situation, which would suggest possibly adverse effect of the treatment. We are expecting less than 1 participant to progress to HCC in either the placebo or treatment arms during the course of the study [8].

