2.3 Rationale

Hypotheses:

- 1) Participants randomized to simvastatin will experience a decrease from baseline to 6 months in serum AFP-L3% compared to the placebo group.
- 2) Compared to the placebo group, participants randomized to simvastatin will have:
 - a) lower serum AFP levels;
 - b) lower serum IL-6 levels;
 - c) lower serum deoxycholic acid (DCA) levels;
 - d) less liver stiffness;
 - e) lower FIB-4 score; and
 - f) lower MELD score.

HCC is amenable to a chemoprevention strategy. Cirrhosis is the penultimate step of the multistage pathogenesis of HCC [4, 5]. Currently, the only clinical option for cirrhotics awaiting a transplant is to watch and wait for HCC to develop and hope that the tumor is caught early enough so that transplantation is still a viable option. In a recent paper, in a convenience sample including Child class B/C patients with chronic liver disease attending a hepatology clinic (similar to recruitment methods for this trial), the 3-year cumulative HCC incidence was 14.8%. Although the data are not presented explicitly, based on the Kaplan-Meyer plot, the cumulative incidence over the first 6-months of follow-up appears to be around 1% [8]. For this current trial, this would amount to less than 1 participant. An intervention that has the ability to delay or halt the development of HCC in the high risk setting of cirrhosis would have a major clinical impact for individual patients, better utilization of precious donor organs, and an improvement of outcomes for this liver disease cohort in aggregate. In spite of this unmet need, chemopreventive strategies for HCC have been understudied in clinical trials.

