8.1 Primary Endpoint

The primary endpoint is change in serum AFP-L3% from baseline to 6 months following treatment initiation. We hypothesize that participants randomized to simvastatin will experience a decrease from

baseline to 6 months in serum AFP L3% compared to the placebo group. In the treatment group, we expect change of 2.8%, with standard deviation=5.3% in both groups (or smaller). A 2.8% decline is clinically relevant given that prior studies report higher differences (7.9%) in AFP-L3% between cirrhotics without HCC and cirrhotics who progress to HCC [50].

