8.2 Secondary and Exploratory Endpoints

Secondary endpoints include additional measures of liver function and disease progression. Changes in secondary endpoints from baseline to 6 months follow-up will be compared between the simvastatin and placebo groups using a similar approach to the main endpoint.

8.2.1 Change in serum AFP. We hypothesize that participants randomized to simvastatin will experience a decrease from baseline in serum AFP levels compared to the placebo group.

8.2.2 Change in serum IL-6. We hypothesize that participants randomized to simvastatin will experience a decrease from baseline in serum IL-6 compared to the placebo group.

8.2.3 Change in serum deoxycholic acid (DCA) levels. We hypothesize that participants randomized to simvastatin will experience a decrease from baseline in serum DCA (deoxycholic acid) levels compared to the placebo group.

8.2.4 Change in liver stiffness. We hypothesize that participants randomized to simvastatin will experience a decrease from baseline in liver stiffness compared to the placebo group.

8.2.5 Change in FIB-4 score. We hypothesize that participants randomized to simvastatin will experience a decrease from baseline in FIB-4 score compared to the placebo group.

8.2.6 Change in MELD score. We hypothesize that participants randomized to simvastatin will experience a decrease from baseline in MELD score compared to the placebo group.

Exploratory endpoints include additional measures of other serum bile acids and immune markers. Differences in exploratory endpoints from baseline to 6 months follow-up will be compared in the simvastatin and placebo groups using a similar approach to the main endpoint.

8.2.7 Change in serum bile acids.

8.2.8 Change in serum immune markers.

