13.5 Secondary and Exploratory Objectives, Endpoints, Analysis Plans

For the continuous secondary endpoints (serum AFP, IL-6, serum DCA, liver stiffness, FIB-4 score, and MELD score) and exploratory endpoints, we will consider D(T) and D(P) as well as percent change relative to baseline, namely, D(T)/B(T) and D(P)/B(P). Biomarker levels at baseline and 6 months, as well as changes from baseline to 6 months, will be summarized using descriptive statistics and graphical methods. ANCOVA models with post-treatment value as the outcome, and treatment group and baseline value as predictors will be used to examine treatment differences. In these models, the estimated coefficient for treatment is the difference between the mean change scores of each arm [116]. Model fit will be assessed using standard model diagnostics including residual plots, influence statistics, and model assumptions such as normality and equivariance, will be verified. Potential outliers will be identified and reasons for extreme values will be investigated. Biomarker values may be transformed, e.g. logarithmically, to satisfy the normality assumption. Interaction between treatment group and baseline will be tested. Additional models that further adjust for other baseline characteristics, including routine clinical tests that have been shown to be strongly predictive of HCC diagnosis in prospective cohorts of cirrhosis such as higher alkaline phosphatase [6], lower platelets [6, 71, 73, 117], lower albumin [73, 118], and lower prothrombin activity [119]. We will also consider clinical variables representing important HCC risk factors captured through the epidemiological questionnaire (Appendix F), including body mass index, current alcohol use, and current dietary fat, carbohydrate, fiber, coffee, and antioxidants [99-112]. The change in variable criterion will be used to identify confounders for our final models. Model selection will be performed using the purposeful model selection approach [120], resulting in a parsimonious model that includes adequate control for confounding. Adjusted treatment effects will be

reported.

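### Section 13.4 states the one-sided AFP-L3% hypothesis and failure rule in the opposite direction to Sections 2.3 and 8.1; once that is corrected, one pre-specified rank test of change adjusted for baseline may add power at little cost

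*Combined protocol and SAP*

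**What the plan says.** Section 13.4 defines D as the 6-month value minus the baseline value, in the simvastatin group (T) and the placebo group (P). It then states: "We will use a nonparametric two-sample Wilcoxon-Mann-Whitney test to address the hypothesis" of equal means "versus H1: means[D(T)] > mean [D(P)] and report a defined one-sided p-value". A p-value below 0.1 counts as evidence of an effect. Otherwise: "If p>0.1 we will report the actual means and the corresponding confidence intervals observed and declare the trial had failed". If the placebo mean of D exceeds the simvastatin mean, "which would be unexpected, we will declare the trial failed and discuss possible explanations for the observed situation", and the plan reads that result as possible harm. Table 2 gives power 0.81 for 36 per arm, means 2.8 and 0, SD 5.3 and alpha 0.1, with the alternative Mean1 > Mean2.

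The hypothesis in Section 2.3 is: "Participants randomized to simvastatin will experience a decrease from baseline to 6 months in serum AFP-L3% compared to the placebo group". Section 8.1 repeats it and justifies the effect size as a 2.8% decline.

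On baseline, Section 13.5 plans for the secondary and exploratory endpoints: "ANCOVA models with post-treatment value as the outcome, and treatment group and baseline value as predictors will be used to examine treatment differences". AFP-L3% is not among them. Section 8.2 says that changes in the secondary endpoints "will be compared between the simvastatin and placebo groups using a similar approach to the main endpoint", but no section makes baseline a covariate for AFP-L3%. Baseline AFP-L3% is measured in every participant at Study Visit 1.

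**The concern.** With D as after minus before, a fall on simvastatin means that D is lower on simvastatin than on placebo. The one-sided test in Section 13.4 looks for the reverse, and its failure rule is triggered by the result the trial hopes to see. The p-value decides success, so the sign decides the conclusion.

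The second matter is efficiency. About 72 patients will be analysable and the trial is declared failed if p exceeds 0.1. Baseline AFP-L3% limits how far a patient can fall: Section 2.3 reports a median of 0.5% in cirrhosis without HCC, which is also the assay's analytic sensitivity. A test that takes account of baseline could recover power from data already collected. That helps only once the direction is right.

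**Working it through.** **Inputs.** From Section 13.4 and Table 2: difference 2.8, SD of change 5.3, 36 per arm, one-sided 0.10. From Section 2.3: AFP-L3% median 0.5, quartiles 0.5 and 1.7, 8.4% of patients above 10, assay limit 0.5. Not given in the documents: the baseline to 6-month correlation ρ, which is therefore varied.

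**Step 1: reproduce 0.81.** Standardised difference = 2.8 / (5.3 × √(2/36)) = 2.241. With the Wilcoxon efficiency for normal data, 2.241 × √(3/π) = 2.190. Power = Φ(2.190 − 1.2816) = 0.818. Direct simulation of the test gives 0.813. The stated 0.81 holds for a test aimed at the true direction.

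**Step 2: the test as written, if the truth is a 2.8-point fall.** Success probability = P(Z > 1.2816 + 2.190) = 0.00026, about 0.0003. Simulations gave 0 to 0.0004. Adjusting for baseline in the same direction does not help.

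**Step 3: what baseline adjustment could add, direction corrected, normal data.** With equal SD σ at both times, the variance of change is 2σ²(1 − ρ), and the variance of the 6-month value given baseline is σ²(1 − ρ²). Their ratio is (1 + ρ)/2. Holding the SD of change at 5.3, the adjusted SD is 5.3 × √((1 + ρ)/2), which gives a benchmark for linear adjustment on the raw scale. The last column is the simulated power of the recommended test: residuals of the ranks of D regressed on the ranks of baseline, fitted without treatment, then a one-sided Wilcoxon test.

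| Assumed ρ | Adjusted SD | Benchmark power (unadjusted 0.818) | Recommended test (unadjusted about 0.81) |
|---|---|---|---|
| 0.3 | 4.27 | 0.924 | about 0.90 |
| 0.5 | 4.59 | 0.894 | about 0.87 |
| 0.7 | 4.89 | 0.863 | about 0.84 |
| 0.9 | 5.17 | 0.833 | no material gain |

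**Step 4: data with a floor.** The normal model ignores the assay limit, so a floored baseline was built to match the Section 2.3 figures: 50% at 0.5, 25% log-uniform from 0.5 to 1.7, 16.6% log-uniform from 1.7 to 10, and 8.4% above 10 with an assumed mean of 17.5. Its mean is 2.74. With a 50% or 70% reduction on simvastatin, under multiplicative or additive noise, the recommended test gained from 0 to about 11 points. The largest shortfall against the planned test was 0.001. Its type I error was 0.096 to 0.107.

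**Step 5: why the form of adjustment matters.** The obvious alternative is a Wilcoxon test on residuals of log 6-month value on log baseline. On the same floored baseline with a 50% reduction:

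| Noise (assumed) | Planned test | Log residuals |
|---|---|---|
| Multiplicative, log-scale SD 0.8 | 0.900 | 0.947 |
| Additive, SD 1 | 0.847 | 0.834 |
| Additive, SD 2 | 0.628 | 0.526 |
| Additive, SD 3 | 0.504 | 0.397 |
| Additive, SD 5.3 | 0.349 | 0.282 |

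The log version gains in the first row and loses about 10 points at additive SD 2 and 3. At additive SD 2, adjusting the ranks of change gives 0.734 against 0.628 for the planned test.

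**The case against.** On direction, the best defence is that this is a drafting slip. Sections 2.3 and 8.1 make the intent plain, and Table 2 makes sense if 2.8 is the size of a fall. That is fair as to intent. But Section 13.4 defines D explicitly and carries the reversed sign through both the alternative and the failure rule, so its text cannot be followed without contradicting the hypothesis. A reader might infer that the trial is bound to fail, or that the power calculation is wrong. The documents support neither: 0.81 is right for the intended direction, and the 0.0003 applies only if the text is followed literally.

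On efficiency, the objection is stronger. An unadjusted rank test on change is a defensible choice and holds its error rate. The gain rests on a correlation that the documents do not give, and normal-data figures are optimistic for a marker with half its values at the assay limit. All of this stands, so the second point is an improvement and not an error.

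Two further inferences should be resisted. One is that any adjustment helps, for instance on the log scale or by carrying over the Section 13.5 model: the log-residual test can lose about 10 points and leaves the percentage-point scale of Section 8.1. The other is that adjustment cures the floor: a patient at 0.5% still cannot show a fall.

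**Conclusion.** The direction in Section 13.4 is wrong as written and contradicts Sections 2.3 and 8.1. Taken literally, the test would declare a true 2.8-point fall a success about 3 times in 10,000, on the plan's own effect, SD, sample size and alpha.

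The baseline point is a cheap improvement. On normal data it is worth about 9, 6 or 3 points of power (from about 0.81) at assumed correlations of 0.3, 0.5 or 0.7, and essentially nothing at 0.9. On the floored data assumed here it is worth 0 to about 11 points. These results hold for adjusted ranks of change, not for every form of baseline adjustment.

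**What to change.** 1. Restate the alternative in Section 13.4 as mean D(T) < mean D(P), reverse the failure rule to match, and label Table 2 as power of the unadjusted test for a fall on simvastatin.
2. Name one primary test: rank D and rank baseline AFP-L3% over all patients, regress the first on the second without treatment in the model, and apply the one-sided Wilcoxon test at 0.10 to the residuals. Allow no switch that depends on diagnostics.
3. Keep the unadjusted Wilcoxon test on change as a sensitivity analysis.
4. Report the difference in mean change in percentage points with a confidence interval whatever the p-value. Section 13.4 promises means and intervals only when p exceeds 0.1, and a rank test gives no estimate to set against the 2.8-point target.
5. Lock all of this before AFP-L3% results are released. Section 9.1 has the assays run in one batch after all 6-month visits, and Section 6.8 gives the study statistician the unblinded randomization log.

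**Cost.** No new visits, samples or assays. The change needs an amendment approved by DCP and the CIRB (Section 14.3), which the direction requires anyway. The adjusted test is slightly harder to explain, and its gain may be nil. If the sponsor prefers to keep the unadjusted test, items 1 and 4 should still be done.

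### The primary one-sided test and the failure rule in Section 13.4 run opposite to the hypothesised benefit: with change defined as After minus Before, a fall in AFP-L3% on simvastatin counts as failure.

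*Combined protocol and SAP*

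**What the plan says.** The direction of benefit is stated twice. Section 2.3 gives the primary hypothesis: "Participants randomized to simvastatin will experience a decrease from baseline to 6 months in serum AFP-L3% compared to the placebo group". Section 8.1 repeats it and adds: "A 2.8% decline is clinically relevant". Section 2.3 also explains why lower is better, since raised AFP-L3% predicts hepatocellular carcinoma.

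Section 13.4 sets out the primary analysis in four pieces:

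- The change score: "we will consider changes D(T) and D(P) for D=After-Before", with T for simvastatin and P for placebo.
- The one-sided Wilcoxon-Mann-Whitney alternative: "versus H1: means[D(T)] > mean [D(P)] and report a defined one-sided p-value". A p-value below 0.1 is taken as evidence of an effect of simvastatin. A p-value above 0.1 means the trial has failed.
- A second failure rule: "If we observe: mean[(D(P)] > mean[D(T)] which would be unexpected, we will declare the trial failed". The plan says of this outcome, "which would suggest possibly adverse effect of the treatment".
- Table 2: power 0.81 with 36 per arm, alpha 0.1, Mean1 2.8, Mean2 0, both SDs 5.3, and the alternative Mean1>Mean2.

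**The concern.** With D as After minus Before, a fall in AFP-L3% gives a negative D. The hypothesised benefit is therefore mean D(T) < mean D(P). The written alternative is the reverse, a relative rise on simvastatin. The second failure rule is reversed as well: it attaches failure and possible harm to the pattern that Sections 2.3 and 8.1 predict.

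This is the only primary test and the only stated rule for calling the trial a failure. A one-sided test needs one direction fixed in advance, and the written direction is the wrong one. If the direction is settled only once results are available, nobody can show that the choice was independent of the data. That matters more here because the study statistician manages the data (Section 12.1) and holds a copy of the unblinded randomization log (Section 6.8).

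**Working it through.** **Inputs.** From Section 13.4: difference 2.8, SD 5.3 in each arm, one-sided alpha 0.10, Wilcoxon-Mann-Whitney test, D = After minus Before. From Section 13.3: 36 analysed per arm. From Sections 2.3 and 8.1: benefit is a decline, so the design effect in the D scale is D(T) = -2.8 and D(P) = 0.

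**Step 1: reproduce the stated power.** Under normality the Mann-Whitney test has efficiency 3/π relative to the z-test, so the effective n per arm is 36 × 3/π = 34.38.

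- Standardised difference: 2.8 / (5.3 × √(2/34.38)) = 2.190.
- Power: Φ(2.190 − 1.282) = Φ(0.908) = 0.818.
- The noncentral t version gives 0.815. A simulation of the test itself (40,000 trials, normal changes) gives 0.813.

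All agree with the stated 0.81. A two-sided test at 0.10 would give only 0.70 to 0.72, so Table 2 is a one-sided calculation and direction matters.

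**Step 2: apply the rules as written to the planned benefit, D(T) = -2.8.**

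- Chance of p<0.1 for the alternative D(T) > D(P): Φ(−2.190 − 1.282) = Φ(−3.472), about 0.0003. The simulation gives 0.0003.
- The p>0.1 route to failure is therefore taken in 1 − 0.0003 = 99.97% of trials.
- Chance that mean D(P) exceeds mean D(T), the second failure rule: Φ(2.8 / (5.3 × √(2/36))) = Φ(2.8/1.249) = Φ(2.241) = 0.987. The simulation gives 0.988.

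**Step 3: compare the scenarios in the simulation.**

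| True state | p<0.1, direction as written | p<0.1, direction reversed | Second failure rule met |
|---|---|---|---|
| Benefit, D(T) = -2.8 | 0.03% | 81.4% | 98.8% |
| Harm, D(T) = +2.8 | 81.3% | 0.03% | 1.3% |
| No effect | 9.9% | 10.0% | 49.8% |

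**Step 4: the cost of leaving the direction open.** If either direction could be adopted after the fact, the false-positive rate under no effect is the sum of the two one-sided rates, 9.9% + 10.0%, or about 20% rather than the planned 10%.

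**Step 5: look for a reconciling passage.** Table 2, the alternative and the failure rule would all fit the hypothesis if change were scored as Before minus After. No section defines it that way, and none reverses the test.

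**The case against.** The strongest reply is that the intent is plain and the slip may be a single one. The alternative, the failure rule, its description as unexpected and possibly adverse, and Table 2 all agree with each other, and with Sections 2.3 and 8.1, if change is scored as a reduction. On that reading only the definition of D is transposed, and no sensible analyst would call a fall in AFP-L3% harmful. The plan also speaks of evidence of an effect, not of success, and this is a Phase II trial that calls itself preliminary.

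Much of this is fair. The likely origin is a decline entered in Table 2 as a positive number, though that is an inference. The inverted outcome follows from a literal reading; it is not a forecast of what the analysts would do. A p<0.1 for a worsening would be labelled an effect, not a benefit.

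None of it removes the contradiction. Whichever element was the slip, the definition, the alternative and the failure sentence cannot all stand beside the stated hypothesis. A clear intention does not replace a correct prespecified direction for a one-sided primary test, because a silent correction after the results would look like a choice made on the data.

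**Conclusion.** The concern holds. As written, the primary decision rule inverts the trial's conclusion. A drug that works as planned reaches p<0.1 in about 0.03% of trials and meets the failure-with-possible-harm rule in about 99%. A drug that worsens AFP-L3% by the same amount reaches p<0.1 in about 81%.

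The percentages assume normal change scores with SD 5.3 and 36 analysed per arm. AFP-L3% is likely to be skewed, with many values at the assay floor: Section 2.3 cites a median of 0.5% in cirrhotics without cancer, which is also the assay's analytic sensitivity. That would alter the power figures but not the direction error, which follows from the definitions alone. This must be corrected before the primary analysis.

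**What to change.** Keep D as After minus Before and change three things in Section 13.4:

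1. Write the alternative as mean D(T) < mean D(P), and state that the one-sided p-value is taken in that direction.
2. Reverse the failure and possible-harm sentence so that it applies when mean D(T) > mean D(P).
3. In Table 2, enter Mean1 as -2.8 and the alternative as Mean1<Mean2. Say in the text, and in Section 8.1, that the expected change is a decrease of 2.8 points.

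Redefining D as Before minus After would also restore consistency in Section 13.4, but it is the weaker option. Section 13.5 reuses D(T) and D(P), and divides them by baseline for percent change, without defining D again. The sign of those summaries would flip unless Section 13.5 were given its own definition.

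The cost is a few lines of text and one table. With the direction corrected, simulated power is 81.4%, so the stated 0.81, the 72 analysed and the 80 randomised all stand. Section 9.1 has AFP-L3% assayed in a single batch after every participant has completed the 6-month visit, so an amendment dated before that assay would be demonstrably independent of the primary results.

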may represent this early malignant phenotype. Additionally, fucosylated proteins may be directly related to the activation of the canonical β -catenin signaling pathway, which is often activated in HCC, suggesting a direct relationship between the alteration in glycosylation with activation of known cancer pathways [55]. The fact that AFP-L3% is widely used as a serum marker for early recognition of HCC, coupled with studies illustrating that AFP-L3 reflects biological features of HCCs, opens that possibility that AFP-L3% is a marker for biological activity important in the etiology of HCC, and may serve as an intermediate marker for chemoprevention studies for HCC.

Although the evidence is lacking with respect to statin influence on AFP-L3%, there is evidence that statins can reduce AFP. In a small randomized control trial including ~80 patients with HCC, 6 months of pravastatin (40 mg/day) was associated with significantly lower AFP levels (p=0.04) and HCC diameter (p=0.03) compared to controls [56]. By extension, statin should also reduce AFP-L3% levels, and given that AFP-L3% is a more specific marker for HCC, we feel that AFP-L3% is best suited to serve as a primary endpoint for this study. We will examine AFP as a secondary endpoint.

[figure not shown]
AFP and AFP-L3 will be measured simultaneously by Quest Diagnostics using an immunofluorescent liquid-phase binding assay. Ion exchange chromatography will be employed to separate AFP-L3 and non-AFP-L3 glycoforms. Fluorescence detection of the 2 chromatography fractions will be conducted. The analytic sensitivity of the assay is 0.8 ng/mL for AFP and 0.5% for AFP-L3%. The reference ranges for AFP are 1.6-4.5 ng/mL, and for AFP-L3% are 0.5-9.9%. For cirrhotics without HCC, median AFP-L3% levels have been reported at 0.5% (25th and 75th quartiles: 0.5,1.7%) [50]. Abnormal is typically defined at >10%, and 8.4% of cirrhotics without HCC were abnormal in that prior study. In the same study, among cirrhotics who went on to develop HCC, the median for AFP-L3% was 6.1% (25th and 75th quartiles: 0.7, 21.3%). Based on a >10% cutoff, 44.1% of those who went on to develop HCC were abnormal [50].

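### Section 13.4 decides by a rank test but also lets the untested sign of the observed means declare failure and possible harm, and the interval it promises does not belong to the test

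*Combined protocol and SAP*

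**What the plan says.** Section 13.4 defines D as the 6-month value minus the baseline value and plans a "two-sample Wilcoxon-Mann-Whitney test to address the hypothesis H0: mean [D(T)] =mean [D(P" (the sentence goes on to a one-sided alternative, also in means). The analyst is to "report a defined one-sided p-value", with alpha 10%. Three decision sentences follow.

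- p below 0.1 counts as evidence that simvastatin affects AFP-L3%.
- For p above 0.1: "If p>0.1 we will report the actual means and the corresponding confidence intervals observed and declare the trial had failed". No confidence level or method is given, and it is not said whether the intervals are per arm or for the difference.
- If the observed placebo mean of D exceeds the simvastatin mean, the trial is declared failed, "which would suggest possibly adverse effect of the treatment". No p-value, interval or threshold is attached.

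Nothing says which sentence prevails if the first and third both apply. Sections 8.1 and 13.8 do not settle it. On the distribution, Section 2.3 cites one earlier study of cirrhosis without HCC, where "median AFP-L3% levels have been reported at 0.5% (25th and 75th quartiles: 0.5,1.7"%), the analytic sensitivity is 0.5%, and 8.4% of patients were above the 10% cutoff.

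**The concern.** A rank test does not test equality of means. It responds to whether a change in one arm tends to be lower than a change in the other. With normal data of equal spread the two questions coincide. With data piled up at an assay floor and a long upper tail they need not. If the cited quantiles carry over, about 0.084 × 36 = 3 patients per arm lie in the upper tail. They can largely set the mean while the others largely set the ranks.

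Two things are at stake. First, an untested sign can add a suggestion of harm to the primary result, or overturn a significant one. Second, the only interval 13.4 promises belongs to a different statistic from the one that decides, and 13.4 plans no estimate or interval at all after a success. The primary conclusion could then depend on which sentence of 13.4 is applied.

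**Working it through.** **Inputs.** From 13.3 and 13.4: 36 per arm, 1:1, one-sided alpha 0.10, mean change 2.8 versus 0, SD 5.3. From 2.3: median 0.5%, quartiles 0.5% and 1.7%, floor 0.5%, 8.4% above 10%. Below, favourable means in the direction the test is meant to detect.

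**Step 1: the plan's own figure.** Power ≈ Φ(δ / (SD·√(2/n)) · √(3/π) − z₀.₉₀).
- SD·√(2/n) = 5.3 × √(2/36) = 1.249, and 2.8 / 1.249 = 2.241.
- 2.241 × √0.955 = 2.190, and 2.190 − 1.282 = 0.909.
- Φ(0.909) = 0.818. Simulating the rank test itself on normal data (40,000 trials) gives 0.811.

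Table 2's 0.81 is reproduced as a one-sided figure and is not in dispute.

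**Step 2: the sign rule with no drug effect.** If D has the same distribution in two independent arms of equal size, swapping the arms changes nothing. The difference in observed means is therefore symmetric about 0, and each sign has probability 1/2 (apart from exact ties). This needs no model. Simulation gives 0.495 for normal data and 0.496–0.499 for skewed data. Among those unfavourable-sign trials, a 90% interval for the difference in means still includes 0 in 90–92%. An opposite one-sided Wilcoxon test at 0.10 would fire in about 10% of null trials.

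**Step 3: conflicts between the sentences.** Two skewed models were assumed, because the documents give baseline quantiles but no distribution of change.
- Lognormal matched to the median and upper quartile, floored at 0.5%, log-scale pre/post correlation 0.7–0.9, drug halves levels. 20,000 trials per setting.
- Mixture: 50% at 0.5; 25% uniform on 0.5–1.7; 16.6% log-uniform on 1.7–10; 8.4% log-uniform on 10–40. Within-person log SD 0.3–0.8, 10–30% of floor patients leave the floor, drug cuts the excess above the floor by 30%. 1,500 trials per setting, so the Monte Carlo standard error is at most √(0.16 × 0.84 / 1,500), just under 1 percentage point.

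| Model, with a drug effect | p<0.1 but unfavourable mean | p>0.1 but interval for the difference in means excludes 0 on the benefit side: 80% / 90% / 95% |
|---|---|---|
| Normal, Table 2 | 0 of 40,000 | 3.2% / 0.2% / 0.01% |
| Lognormal | 5.3–6.0% | 4.4–7.3% / 1.5–2.2% / 0.4–0.5% |
| Mixture | 1–2.5% | 9–16% / 4–7% / 1–2% |

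With no drug effect the first conflict occurs in 1.1–1.4% of lognormal trials, 1.2% of mixture trials, and none under normality.

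**The case against.** The sign rule rarely changes pass or fail. When p>0.1 the trial has already failed and the rule only adds wording. That wording is soft: it asks for discussion and triggers no safety action, since safety is handled in 8.5 and 13.7. The skewed models are assumptions resting on one earlier study. The lognormal puts 4.9% above 10% against the cited 8.4%, and its SD of change is 4.9–7.5. The mixture's central SD is about 3.4. The plan assumes 5.3 or smaller. All of this stands, and it limits the size. It does not remove the 50% figure, which needs no model.

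A reader might infer that verdict and interval would clash far more often, by also counting significant results whose interval for the means includes zero. The documents do not support that: 13.4 promises an interval only when p>0.1, so no interval stands beside a success unless an analyst adds one. Nor can any single clash rate be attributed to the plan, because no level is stated. If the intervals are per arm, they cannot exclude zero for the difference at all.

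A reader might also infer that a successful trial would report nothing beyond a p-value. Section 13.5 does plan descriptive summaries of biomarker levels and changes. However, that section covers secondary and exploratory endpoints and its list omits AFP-L3%, so its reach is arguable, and its ANCOVA is not assigned to the primary endpoint.

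Finally, with D as after minus before, the alternative and the sign rule run against the decrease hypothesised in 2.3 and 8.1. That is a separate matter. Correcting the direction would leave the untested sign rule and the mismatched interval in place.

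**Conclusion.** The point holds at moderate weight. The firm part is that the sign rule would suggest a possibly adverse effect in about half of trials of a drug with no effect, for any distribution, given the equal arms planned. The model-dependent parts are smaller. A significant result contradicted by the means is essentially absent under Table 2's normal model and occurs in about 1–6% of trials under the assumed skewed models. A declared failure beside an interval for the difference that excludes zero on the benefit side occurs, with a working drug, in roughly 3–16% of trials at 80%, 0.2–7% at 90% and at most about 2% at 95%. The spread across levels is itself a result of the unstated level. The power calculation is not in error.

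**What to change.** In Section 13.4:

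1. Write the null hypothesis as equal distributions of D in the two arms. Base the verdict only on the one-sided Wilcoxon test in the hypothesised direction (decrease), and reconcile the notation with Sections 2.3 and 8.1.
2. Delete the sign-of-the-mean rule. Speak of a possibly adverse effect on AFP-L3% only if the opposite one-sided Wilcoxon test gives p<0.1. That lowers the null rate from about 50% to about 10%.
3. Whatever the p-value, report the Mann-Whitney probability that a simvastatin change is lower than a placebo change, counting ties as half, with an 80% two-sided interval, which matches a one-sided 0.10 test. In the mixture simulation an interval-type test of this kind disagreed with the Wilcoxon verdict in at most 0.5% of trials. Give means and medians by arm as description.

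The cost is a few lines of plan text and R code. The sample size and the stated power of 0.81 stay as they are. The small downside is that the difference in means is no longer the headline estimate.
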